9.5 Analysis Populations

9.5.1 Immunogenicity Analysis Populations

The Per-Protocol Immunogenicity (PPI) population will serve as the primary population for the analysis of immunogenicity data in this study. The PP population is defined as participants who receive the 3 scheduled doses of study vaccines, adhere to guidelines for administration of study vaccines, provide baseline and post-vaccination blood samples within

acceptable day range, and do not have important deviations from the protocol that may substantially affect the results of the primary endpoint.

The final determination on important protocol deviations, and thereby the composition of the PP population, will be made prior to the final database lock.

Supportive analysis for primary immunogenicity objective will be performed on the full analysis set (FAS) of all participants who provide baseline and post dose 3 serum samples, regardless of protocol deviations.

Participants will be included in the treatment group to which they are randomized for the analysis of immunogenicity data using both the PP and FAS populations.

9.5.2 Safety Analysis Populations

Safety Analyses will be conducted in the All Participants as Treated (APaT) population, which consists of all randomized participants who receive at least one dose of study vaccination. Participants will be included in the group corresponding to the study vaccination they actually received for the analysis of safety data using the APaT population.

At least one temperature measurement obtained subsequent to study intervention is required for inclusion in the analysis of temperature.

9.6 Statistical Methods

Statistical testing and inference for immunogenicity and safety analyses are described in Section 9.6.1 and Section 9.6.2, respectively. Unless otherwise stated, all statistical tests will be conducted at the $\alpha=0.025$ (1-sided) level.

9.6.1 Statistical Methods for Immunogenicity Analyses

This section describes the statistical methods that address the primary and secondary immunogenicity objectives. Methods related to exploratory objectives will be described in the supplemental SAP.

Primary Endpoint

For the primary hypothesis, seroconversion percentage at 1 month post dose 3 of IPV will be analyzed separately for each of 3 poliovirus types. The statistical criterion for non-inferiority requires that the lower bound of two-sided 95% confidence interval of the difference in seroconversion percentages (concomitant-use group minus staggered-use group) be greater than -10% for each poliovirus type. The primary hypothesis will be considered a success if the non-inferiority criteria for the difference in seroconversion percentages are met for all 3 poliovirus types in the comparisons between concomitant-use group vs. staggered-use group.

For each poliovirus type, the hypothesis to be tested at $\alpha=0.025$ level (1-sided) are

$$H_0: p_1 - p_2 \leq -0.1$$

$$H_a: p_1 - p_2 > -0.1$$

where p_1 is the true seroconversion percentage at 1 month post dose 3 in the concomitant-use group and p_2 is the true seroconversion percentage at 1 month post dose 3 in the staggered-use group. The confidence interval will be calculated using the method proposed by Miettinen and Nurminen [Miettinen, O. and Nurminen, M. 1985].

Secondary Endpoints

For the proportion-type estimates of the secondary endpoints such as seroresponse rates of neutralizing antibodies to poliovirus types 1, 2, and 3, the 95% CIs of within each group will be provided and obtained by using exact binomial method proposed by Clopper and Pearson (1934) [Clopper, C. J. 1934].

The evaluation of IPV neutralizing antibody GMTs to each of poliovirus types 1, 2, and 3 will include descriptive summaries and within-group 95% CIs. Point estimates for the GMTs will be calculated by exponentiating the estimates of the mean of the natural log values. The within-group CIs will be derived by exponentiating the CIs of the mean of the natural log values based on the t-distribution.

Summary statistical analysis will be provided for exploratory endpoints. Details will be described in the supplemental SAP.

Table 3 summarizes the key immunogenicity analyses.

Table 3 Analysis Strategy for Key Immunogenicity Variables

Endpoint/Variable (Description, Time Point)	Primary vs. Supportive Approach [†]	Statistical Method [‡]	Analysis Population	Missing Data Approach
Primary Objectives				
Neutralizing Antibody Seroconversion Percentages to Each of Poliovirus Types 1, 2, and 3 at 1 Month Post Dose 3 of IPV (each type will be tested separately)	P	Point and 95% CI estimation as well as statistical testing of binomial proportion based on M & N method [§]	PP	Observed data only
Neutralizing Antibody Seroconversion Percentages to Each of Poliovirus Types 1, 2, and 3 at 1 Month Post Dose 3 of IPV	S	Point and 95% CI estimation as well as statistical testing of binomial proportion based on M & N method [§]	FAS	Observed data only

Endpoint/Variable (Description, Time Point)	Primary vs. Supportive Approach [†]	Statistical Method [‡]	Analysis Population	Missing Data Approach
Secondary Objectives				
Neutralizing Antibody GMTs to Each of Poliovirus Types 1, 2, and 3 at 1 Month Post Dose 3 of IPV	P/S	Point and 95% CI estimation based on t-distribution of natural log values	PP/FAS	Observed data only
Proportions of Participants with Neutralizing Antibody Titer \geq 1:8 at 1 Month Post Dose 3 of IPV for Each of Poliovirus Types 1, 2, and 3	P/S	Point and 95% CI estimation based on exact method [%]	PP/FAS	Observed data only
Proportions of Participants with Neutralizing Antibody Titer \geq 1:64 at 1 Month Post Dose 3 of IPV for Each of Poliovirus Types 1, 2, and 3	P/S	Point and 95% CI estimation based on exact method [%]	PP/FAS	Observed data only
[†] P=Primary approach; S=Supportive approach. [‡] Statistical models are described in further detail below: [§] Miettinen and Nurminen method. [%] Exact binomial method proposed by Clopper and Pearson (1934).				

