3 HYPOTHESES, OBJECTIVES, AND ENDPOINTS

In healthy Chinese infants 48-63 days of age:

Objectives	Endpoints
Primary	

Objective: To demonstrate that the immunogenicity of IPV in the concomitant-use group is non-inferior to that in the staggered-use group. Hypothesis (H1): The seroconversion percentage at 1 month post dose 3 for each of poliovirus types 1, 2, and 3 in the concomitant-use group is non-inferior to those in the staggered-use group. The statistical criterion for non-inferiority requires that the lower bound of two-sided 95.0% confidence interval for the difference (concomitant-use group minus staggered-use group) in seroconversion percentages be greater than -10% for each poliovirus type.	
Neutralizing antibody seroconversion to each of poliovirus types 1, 2, and 3
Secondary	

Objective: To evaluate immune responses to IPV at 1 month post dose 3 in the concomitant-use and staggered-use groups as measured by geometric mean titers (GMTs) of neutralizing antibodies to poliovirus types 1, 2, and 3.Objective: To evaluate immune responses to IPV at 1 month post dose 3 in the concomitant-use and staggered-use groups as measured by the proportions of participants with neutralizing antibody titer $\geq 1:8$ and $\geq 1:64$ for each of poliovirus types 1, 2, and 3.	
Neutralizing antibody titer to each of poliovirus types 1, 2, and 3Neutralizing antibody responses to each of poliovirus types 1, 2, and 3

Objectives	Endpoints

 Objective: To evaluate the safety of concomitant administration of V260 and IPV based on the proportions of participants experiencing solicited injection-site adverse events (AEs), solicited systemic AEs, and serious AEs (SAEs). 	
 Solicited injection-site AEs (following vaccination of IPV) Solicited systemic AEs SAEs
Exploratory	

 Objective: To evaluate immune responses to V260 at 1 month post dose 3 in the concomitant-use and staggered-use groups using anti-rotavirus type-specific IgA based on GMTs and proportions of participants with ≥ 3-fold increase in titer post-vaccination from baseline. 	
 Anti-rotavirus type-specific IgA antibody responses to rotavirus serotypes G1, G2, G3, G4, and P1A[8]

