4.2 Scientific Rationale for Study Design

This is a post-marketing commitment study. This study is designed to assess immunogenicity of IPV when concomitantly administered with V260 in Chinese infants with the staggered-use group as a comparative control. The immunogenicity of V260 will be evaluated as exploratory objective. The safety of study vaccines will also be evaluated in the study.

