4.2.1 Rationale for Endpoints

4.2.1.1 Immunogenicity Endpoints

The immunogenicity of IPV will be measured using poliovirus serum neutralizing antibody assay of National Institutes for Food and Drug Control (NIFDC, Beijing, China).

The primary endpoints are neutralizing antibody seroconversion percentages to each of poliovirus types 1, 2, and 3 at 1 month post dose 3 of IPV. The seroconversion is defined as antibody titer $\geq 1:8$ post-vaccination in baseline seronegative participants or ≥ 4 -fold increase in titer post-vaccination in baseline seropositive participants, which is consistent with WHO's recommendation on the immunogenicity evaluation of IPV vaccines [World Health Organization Expert Committee on Biological Standards 2014]. The cut-off value for seropositivity is 1:8 for all 3 poliovirus types [Nathanson, N. 2005].

The neutralizing antibody GMTs to each of poliovirus types 1, 2, and 3 at Day 1 prior to vaccination and 1 month post dose 3 of IPV will be summarized as secondary endpoints. In addition, the proportions of participants with neutralizing antibody titer $\geq 1:8$ and $\geq 1:64$ at 1 month post dose 3 of IPV will be summarized for each of poliovirus types 1, 2, and 3, as requested by local regulatory agency.

The immunogenicity of V260 will be measured using anti-rotavirus type-specific IgA assay of NIFDC as exploratory objectives. An immunological correlate of protection has not been

identified for rotavirus disease. The antibody responses to V260 at 1 month post dose 3 will be summarized using the same methods adopted in the prior efficacy study in China, i.e. based on GMTs and proportions of participants with ≥ 3 -fold increase in titer post-vaccination from baseline.

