4.2.2 Rationale for the Use of Comparator/Placebo

To assess the immunogenicity of IPV concomitantly administered with V260, the staggered-use group will be used as a comparative control in the study.

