9.4.1 Immunogenicity Endpoints

A description of immunogenicity assessments is presented in Section 4.2.1.1.

The primary immunogenicity analysis endpoints are neutralizing antibody seroconversion percentages to each of poliovirus types 1, 2, and 3 at 1 month post dose 3 of IPV. The seroconversion is defined as antibody titer $\geq 1:8$ post-vaccination in baseline seronegative participants or ≥ 4 -fold increase in titer post-vaccination in baseline seropositive participants. The cut-off value determining baseline seropositivity is 1:8 for all 3 poliovirus types. Neutralizing antibodies to poliovirus types 1, 2, and 3 will be measured by the laboratory of NIFDC.

The secondary immunogenicity analysis endpoints include:

- Neutralizing antibody GMTs to each of poliovirus types 1, 2, and 3 at 1 month post dose 3 of IPV.
- Proportions of participants with neutralizing antibody titer $\geq 1:8$ and $\geq 1:64$ at 1 month post dose 3 of IPV for each of poliovirus types 1, 2, and 3.

The exploratory immunogenicity analysis endpoints include:

- Proportions of participants with ≥ 3 -fold increase in anti-rotavirus type-specific IgA titer post-vaccination from baseline to serotypes G1, G2, G3, G4, and P1A[8] at 1 month post dose 3 of V260.
- Anti-rotavirus type-specific IgA GMTs to serotypes G1, G2, G3, G4, and P1A[8] at 1 month post dose 3 of V260.

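### The secondary IPV endpoints are planned with within-group intervals only; prespecifying a GMT ratio and between-group differences would be a cheap improvement, not the repair of an error.

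*Combined protocol and SAP*

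**What the plan says.** Section 9.6.1 states that it covers the primary and secondary immunogenicity methods, and it defers only exploratory methods to the supplemental SAP.

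- **GMTs:** "The evaluation of IPV neutralizing antibody GMTs to each of poliovirus types 1, 2, and 3 will include descriptive summaries and within-group 95% CIs". The intervals are t-based on the natural-log scale and back-transformed.
- **Percentages at or above 1:8 and 1:64:** "the 95% CIs of within each group will be provided and obtained by using exact binomial method", that is, Clopper-Pearson.
- **Table 3:** the GMT row reads "Point and 95% CI estimation based on t-distribution of natural log values", and the two percentage rows name the exact method. These rows do not themselves say that the intervals are within group; that follows from the text and from the one-sample methods named. Only the seroconversion rows name Miettinen-Nurminen estimation and testing.

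The secondary GMT objective in Section 3 is descriptive: "To evaluate immune responses to IPV at 1 month post dose 3 in the concomitant-use and staggered-use groups as measured by geometric mean titers". No comparative hypothesis is attached to it. The design rationale is comparative: Section 4.2 describes a study "designed to assess immunogenicity of IPV when concomitantly administered with V260 in Chinese infants with the staggered-use group as a comparative control", and Section 4.2.2 repeats that role for the comparator. Baseline titres are already collected. Section 4.2.1.1 says that GMTs "at Day 1 prior to vaccination and 1 month post dose 3 of IPV will be summarized as secondary endpoints".

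No GMT ratio, and no between-group difference for a secondary IPV endpoint, appears in Sections 1.1, 3, 4.2.1.1, 9.1, 9.4.1, 9.6.1, 9.8 or 9.9.

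**The concern.** The trial asks whether giving V260 on the same day lowers the response to IPV, and it randomises a control group to answer that. Seroconversion is the only IPV endpoint with a planned contrast. It reduces each titre to yes or no, and it is assumed to sit close to its ceiling. GMT keeps the information in the titres but is to be shown as two separate intervals.

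A reader of that table will judge the contrast by whether the two intervals overlap. Non-overlap is a stricter condition than a ratio interval that excludes 1, so a moderate fall in titre for one poliovirus type can look unremarkable in the planned output. A ratio worked out after the results are known would not be prespecified, and the trial is open-label. At stake is how clearly a secondary result is shown, not the study's success criterion.

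**Working it through.** **1. The plan's own figure.** The documents give no power, margin or SD for the secondary endpoints. The only calculation is Table 6, for seroconversion. Inputs from Section 9.9.1: 170 evaluable per group (85% of 200), margin 0.10, one-sided 0.025, equal true rates of 96%, 93% and 97%. Power = Φ[(0.10 − 1.96·s0)/s1]. Here s1 = √(2p(1−p)/170), and s0 is the standard error under the margin-restricted rates.

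- Type 1: (0.10 − 1.96 × 0.02766)/0.02125 = 2.15, power 0.9844 (stated 0.9842)
- Type 2: (0.10 − 1.96 × 0.03125)/0.02767 = 1.40, power 0.9193 (stated 0.9188)
- Type 3: (0.10 − 1.96 × 0.02646)/0.01850 = 2.60, power 0.9954 (stated 0.9953)

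The product of the stated powers is 0.9842 × 0.9188 × 0.9953 = 0.900, as stated. Table 6 reproduces, and nothing below changes it.

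**2. When each display shows a difference.** Assumptions not in the documents: log-normal titres and an equal ln SD in both groups of 1.2, with 1.0 and 1.5 as the range. n = 170 per group.

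- The ratio interval lies below 1 if the observed ratio < exp(−t338 · SD · √(2/170)), with t338 = 1.967. At SD 1.2 this is exp(−0.256) = 0.77.
- The two group intervals separate if the observed ratio < exp(−2 · t169 · SD/√170), with t169 = 1.974. At SD 1.2 this is exp(−0.363) = 0.70.

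On the log scale the second condition is stricter by 0.363/0.256 = 1.42, whatever the common SD.

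**3. Probability of each for a true fall f in one type.** Φ[(−ln(1−f) − threshold)/(SD · √(2/170))]. At SD 1.2 the denominator is 0.130. For f = 0.30, −ln 0.7 = 0.357:

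- ratio interval: (0.357 − 0.256)/0.130 = 0.77, probability 0.78
- separation: (0.357 − 0.363)/0.130 = −0.05, probability 0.48

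| | SD 1.0 | SD 1.2 | SD 1.5 |
|---|---|---|---|
| Ratio interval below 1 if observed ratio under | 0.81 | 0.77 | 0.73 |
| Group intervals separate if observed ratio under | 0.74 | 0.70 | 0.63 |
| 30% fall: ratio interval / separation | 0.91 / 0.69 | 0.78 / 0.48 | 0.59 / 0.27 |
| 20% fall: ratio interval / separation | 0.54 / 0.23 | 0.40 / 0.14 | 0.28 / 0.08 |

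**4. What baseline adjustment adds.** The interval factor is exp(0.256 · √(1−ρ²)) at SD 1.2, where ρ is the assumed correlation of baseline with post-dose ln titre. It is 1.29 at ρ = 0, 1.26 at 0.4 and 1.23 at 0.6.

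**5. Precision of the differences in percentages.** With equal observed counts in both groups of 168, 162 or 153 out of 170, the Miettinen-Nurminen 95% interval is about ±3.2, ±4.9 or ±6.6 percentage points.

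**6. How far the primary criterion protects against a uniform 30% fall.** This needs the two-part definition of Section 9.4.1: reaching 1:8 if seronegative, or a 4-fold rise if seropositive. Assumptions: 50% baseline seropositive, baseline and post-dose ln SD 1.2, control means set to give 96%, 93% and 97%, then a shift of ln 0.7, the exact Miettinen-Nurminen test, and types independent. The probability that all three types pass is 0.30, 0.46 and 0.55 at ρ = +0.4, 0 and −0.4. Over 30% to 70% seropositive and SD 1.0 to 1.5 it runs from 0.21 to 0.64.

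**The case against.** The strongest reply is that the plan does what its objectives ask. The secondary objectives describe responses in both groups, with no hypothesis, margin or power, and within-group estimation fits that. Section 4.2.1.1 says the 1:8 and 1:64 percentages are summarised at the local regulator's request. The comparative-control role is met by the primary analysis, run in the per-protocol population and again in the full analysis set. All of this stands. A reader might infer that the plan contradicts its own comparative design, or that the primary conclusion is weakened; the documents support neither.

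Three further points stand in part.

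- *The ratio can be worked out from the tables.* An unadjusted ratio and an approximate interval can. The baseline-adjusted ratio cannot, and neither would be prespecified.
- *The wording is not exclusive, and a supplemental SAP exists.* True, but Section 9.6.1 assigns that document the exploratory methods, so it cannot be assumed to contain these contrasts.
- *More unadjusted intervals invite over-reading.* With three independent types and no true effect, at least one unadjusted ratio interval falls wholly below 1 with probability 1 − 0.975³ = 0.07. There is no GMT margin against which to judge it. This is a real cost and calls for clear labelling.

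The descriptive wording does not defeat the suggestion, because an estimated ratio without margin or alpha is also descriptive.

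**Conclusion.** The point holds as an optional improvement. For the secondary IPV endpoints the plan gives no prespecified between-group estimate, and its display is less sensitive to a fall in titre than a ratio interval. At an assumed ln SD of 1.2, a true 30% fall would be visible with probability 0.78 in a ratio interval and 0.48 through separated group intervals. These sizes rest on log-normal titres, equal SDs and 170 per group. The direction does not depend on the SD.

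A reader might go further and infer either that the primary criterion would let titre falls through unnoticed or that it would catch most of them. The documents give no titre distribution or baseline seropositivity, so they support neither. Under the assumptions in step 6 the study would still succeed with probability 0.21 to 0.64 after a uniform 30% fall, and the documents do not say whether such a fall matters.

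**What to change.** Before database lock, prespecify the following in the supplemental SAP, as estimation only. Section 9 allows that route for non-confirmatory analyses. Align Section 9.6.1 and Table 3 at the next amendment.

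- **GMT ratio:** for each poliovirus type, the ratio (concomitant/staggered) with 95% CI from an ANCOVA of ln post-dose titre on group and ln baseline titre, in the per-protocol population and the full analysis set, with the unadjusted ratio alongside. State the assay's reporting limit and the value used below it, since the logarithm needs a number and Sections 9.4.1 and 9.6.1 give no such rule.
- **Percentages:** for each type, the between-group differences at or above 1:8 and at or above 1:64, with Miettinen-Nurminen 95% CIs. Keep the 1:8 difference: it does not duplicate seroconversion, which requires a 4-fold rise in infants who are seropositive at baseline.
- **Labelling:** call all of these descriptive and unadjusted for multiplicity, and state that a ratio interval below 1 is not a failed criterion.

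The cost is text and programming, with no new samples, visits, participants or alpha. The downside is up to twelve extra intervals per population (three adjusted ratios, three unadjusted ratios and six differences), with no multiplicity control and no GMT margin. Baseline adjustment itself adds little precision (step 4); the gain is mainly prespecification and a clearer display.

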9.6.2 Statistical Methods for Safety Analyses

Safety and tolerability will be assessed by clinical review of all relevant parameters including AEs and post-vaccination temperature measurements.

An overall assessment of adverse events will be summarized for each group by dose period (dose period is defined in [Table 4](#)) and across all dose periods.

Table 4 Each Group by Dose Period

Dose Period	Concomitant-Use Group (Vaccine administered)	Staggered-Use Group (Vaccine administered)
1	Visit 2 (V260 + IPV)	Visit 1 (V260)
	Visit 3	Visit 2 (IPV)
2	Visit 4 (V260 + IPV)	Visit 3 (V260)
	Visit 5	Visit 4 (IPV)
3	Visit 6 (V260 + IPV)	Visit 5 (V260)
	Visit 7	Visit 6 (IPV)

Summary statistics, counts and percentage without confidence interval, will be provided by group. Proportions of participants with solicited injection-site AEs (following vaccination of IPV), solicited systemic AEs within 7 days following study vaccination will be given. Maximum axillary temperatures recorded on the VRC from Day 1 through Day 7 post-vaccination will be summarized. Table 5 shows the safety endpoints that will be summarized.

Table 5 Analysis Strategy for Safety Parameters

Safety Endpoints	Time Period	Descriptive Statistics
Solicited Injection-Site AEs	Days 1-7 post-vaccination of V260 and IPV in the concomitant-use group, and Days 1-7 post-vaccination of IPV in the staggered-use group, across all dose periods and by dose period	X
Solicited Systemic AEs	Days 1-7 post-vaccination of V260 and IPV in the concomitant-use group, and Days 1-7 post-vaccination of V260 plus Days 1-7 post-vaccination of IPV in the staggered-use group, across all dose periods and by dose period	X
Maximum Axillary Temperature	Days 1-7 post-vaccination of V260 and IPV in the concomitant-use group, and Days 1-7 post-vaccination of V260 plus Days 1-7 post-vaccination of IPV in the staggered-use group, across all dose periods and by dose period	X
Any Injection-Site AEs	Days 1-15 post-vaccination of V260 and IPV in the concomitant-use group, and Days 1-15 post-vaccination of IPV in the staggered-use group, across all dose periods and by dose period	X
Any Systemic AEs	Days 1-30 post-vaccination of V260 and IPV in the concomitant-use group, and Days 1-15 post-vaccination of V260 plus Days 1-15 post-vaccination of IPV in the staggered-use group, across all dose periods and by dose period	X
Any Vaccine-related Injection-Site AEs	Days 1-15 post-vaccination of V260 and IPV in the concomitant-use group, and Days 1-15 post-vaccination of IPV in the staggered-use group, across all dose periods and by dose period	X
Any Vaccine-related Systemic AEs	Days 1-30 post-vaccination of V260 and IPV in the concomitant-use group, and Days 1-15 post-vaccination of V260 plus Days 1-15 post-vaccination of IPV in the staggered-use group, across all dose periods and by dose period	X
Discontinuation due to any AE	Entire Study Period by Vaccination Group	X
Any Serious AEs including Intussusception	Entire Study Period by Vaccination Group	X

X = results will be provided.

To assess the severity of adverse events, both Sponsor's criteria (see "Assessment of Intensity/Toxicity" in Section 10.3 - Appendix 3) and China Regulatory Agency's criteria (see Section 10.7 - Appendix 7: Country-specific Requirements) will be applied. The incidence of greatest adverse event severity reported by a participant based on both the two criteria will be tabulated for: all injection-site AEs and all systemic AEs across all dose periods.

For the across dose-period summaries and analyses, if the same AE occurs multiple times across dose periods, the AE will be counted once. In order to evaluate any additive safety issues for the concomitant use of V260 and IPV compared to the staggered use of these vaccines, the following summaries will also be provided: Frequencies and percentages of the solicited systemic AEs during Days 1 to 7 after V260 concomitant with IPV in the concomitant-use group, during Days 1 to 7 after V260 alone in the staggered-use group, and during Days 1 to 7 after IPV alone in the staggered-use group.

Any injection-site AEs and vaccine-related injection-site AEs during Days 1 to 30 post-vaccination of V260 and IPV in the concomitant-use group will be summarized separately.

Any reportable safety events collected between Visit 1 and 2 in the concomitant-use group will be listed separately.

For serious adverse events observed during the study, including intussusception, a detailed description will be included in the CSR.

